## List of Abbreviations

ADE	Adverse Device Effect
AE	Adverse Event
App	Software Application on smart mobile device
BGMS	Blood Glucose Monitoring System
BP	Blood Pressure
CDE	Certified Diabetes Expert
CRF	Case Report Form
HCT	Hematocrit
EC	Ethics Committee
GCP	Good Clinical Practice
FDA	Food and Drug Administration
IDE	Investigational Device Exemption
IRB	Institutional Review Board
PI	Principal Investigator
SADE	Serious Adverse Device Effect
SAE	Serious Adverse Event
SMD	Smart Mobile Device
SSF	Study Site File
USADE	Unanticipated Serious Adverse Device Effect
LSI	LabStyle Innovation Ltd.

## Protocol Synopsis

Protocol Title:	Digital Self-Management and Health Coaching for Type 2 Diabetes - Impact on Diabetes clinical and wellbeing indicators
Protocol ID:	CP-0010
Principal Investigator:	[name] [name] [contact] Email: [name] <[contact]>
Sponsor:	LabStyle Innovation (LSI) [name]
Sponsor Representative:	[name] [contact] E-mail: [contact]
Product to be Evaluated:	Dario Blood Glucose Monitoring System (BGMS) and connected cloud platform
Research Center:	Diabetes and Endocrinology Consultants of Pennsylvania, LLC (Decpa LLC) [name]
Research Center Representative:	[name]
Data Management & Statistics:	LabStyle Innovation (LSI)
Study Objectives:	To evaluate the impact of the Dario digital self-monitoring platform provided with diabetes management coaching on: 1. Individual's Quality of Life for 2. Clinical parameters (HbA1C, weight, lipids profile, etc.) For people with Type 2 Diabetes at end of study vs. baseline.
Study Design:	single-arm
Study Type	Interventional, Behavioral

Study Specimen:	Lab test Venous blood - Blood glucose level and HbA1C Self-test Capillary whole blood - Blood glucose level
Study Procedures:	Each subject enrolled in the study will be requested to complete an intake questionnaire including diabetes quality of life questions. The subject will use Dario Blood glucose monitoring system and will be contacted by a Certified Diabetes Educator (CDE) two to three times a month as well as have a direct communication using other communication channels such as mail, chat and text messaging (SMS) for lifestyle and diabetes management coaching for a total duration of three months. In the end of study, the subject will complete a diabetes quality of life questionnaire and have a blood test to evaluate its clinical parameters.
Study Population:	Males and females with type 2 Diabetes, ages above 35 recruited through clinic, physician offices, and similar sources having HbA1c level of 8.5% or more, verified by last lab test performed during the last 60 days
Number of Visits	2 visits only
Sample Size:	25 subjects
Data to be Collected:	
 
• QoL questions
 
• Demographic (age, gender, ethnicity, education, etc.)
 
• Diabetes profile: type, time since diagnosis and insulin treatment
 
• Concomitant medications
 
• Medical history
 
• Dario measurement details (test strip lot #, smart mobile device type, Dario meter #)
 
• Capillary whole blood Glucose levels
 
• Venous blood test: HbA1C, Lipid profile, HCT results
 
• Blood Pressure (BP)
 

Inclusion / Exclusion Criteria	
Inclusion Criteria
 
 
1. Adults 35 years of age or older
 
2. Diagnosed type 2 Diabetes
 
3. HbA1C test taken less than 2 months ago and is equal to or above 8.5%
 
4. Able to read, write and understand English
 
5. Have supported smartphone (see appendix C for the full smartphone list) with internet package for their service provider
 
6. The subject is able and agrees to sign the informed consent form
 
 
Exclusion Criteria
 
 
1. Adults with impaired cognition
 

	
 
2. Cohabiting with a participant in the study
 
3. Have an underlying medical condition (such as kidney disease, hemoglobin variants, anemia) that may provide misleading A1C levels
 
4. Subject is critically ill
 
5. Subject has an impairment that prevents him/her from following the study procedures
 
6. Subject is not using medication that may interfere with the blood glucose measurement
 
7. HCT level which are outside Dario BGMS declared range (20%-60%)
 

Analyses & Reports:	Complete analysis and final report after enrolling up to 25 subjects and aiming to have 20 people running the full three months program (after withdrawal) to complete the coaching program that meet the inclusion/exclusion criteria

## 1.0 Introduction

Diabetes is one of the prevailing epidemics of the century. The increasing global prevalence of diabetes is challenging traditional approaches towards diabetes management. Novel self-management tools, which aim to engage patients in daily diabetes care and optimize the role of health care professionals, may facilitate a more robust, scalable, and effective approach to the management of diabetes.

Self-monitoring of blood glucose is a valuable tool for helping patients achieve and maintain target blood glucose levels to reduce the risk of diabetes-related complications. Particularly, frequent self-monitoring of blood glucose is an essential requirement to adequately manage diabetes mellitus type 1 or type 2. When performed and utilized properly, blood glucose meters for self-measurement of blood glucose allow diabetic patients to determine their blood glucose level and to use the information as part of their treatment program.

Health coaching is defined as health education, promotion and support by a medical professional to enhance the well-being of individuals and facilitate the achievement of their health-related goals. Diabetes health coaching is provided by certified diabetes educator (CDE) giving overall guidance related to all aspects of diabetes to increase subject's knowledge and skills about the disease and to promote self-care behaviors for effective self-management and glycemic control.

A connected BGMS with a digital platform that enables real-time accessibility by the health coach to the patient's clinical data, provides an effective way to intervene on real clinical information. Intervention in close proximity to recorded clinical events (e.g. hyperglycemic events, continuous out of range (OOR), etc.) on easy to remember occurrences may lead to more effective life change activities by the patient.

The aim of this study is to evaluate the effect of digital self-monitoring blood glucose and diabetes health coaching, in adults with Type 2 Diabetes and its impact on diabetes clinical and wellness indicators over a period of 3 months.

## 2.0 Device Information

### 2.1 Device Name

Dario Blood Glucose Monitoring System (BGMS) with Dario digital platform providing access to patient's clinical information and logged behavior captured in the BGMS Application (app).

### 2.2 BGMS Intended Use

The Dario Blood Glucose Monitoring System consists of the Dario Blood Glucose Meter,

Dario Glucose Test Strips, Dario Glucose Control Solutions and the Dario App as the display component of the Dario Blood Glucose Monitoring System. The Dario Blood Glucose Monitoring System is intended for the quantitative measurement of glucose (sugar) in fresh capillary whole blood samples drawn from the fingertip. The Dario Blood Glucose Monitoring System is intended to be used by a single person and should not be shared.

The Dario Blood Glucose Monitoring System is intended for self-testing outside the body (in vitro diagnostic use) by people with diabetes at home to monitor the effectiveness of diabetes control. The Dario Blood Glucose Monitoring System should not be used for the diagnosis of or screening of diabetes or for neonatal use.

The Dario Blood Glucose Test Strips are for use with the Dario Blood Glucose Meter to quantitatively measure glucose (sugar) in fresh capillary whole blood samples drawn from the fingertip.

The Dario Control Solutions are for use with the Dario Blood Glucose Meter and the Dario Blood Glucose Test Strips to check that the meter and test strips are working together properly and that the test is performing correctly.

### **2.3 Device Description**

The Dario Blood Glucose Monitoring System (BGMS) by LabStyle Innovation (LSI) is used for measuring blood glucose levels from fresh capillary whole blood samples taken from the fingertip. It consists of a blood glucose meter (dongle), which is connected to a smart mobile device for usage with a dedicated application, disposable test strips stored in a cartridge, a lancing device and lancets.

The Dario™ BGMS has a unique all-in-one feature allowing the holding of all relevant items for glucose self-testing in one small, easy to carry, simple to use lancing device enclosure, while enabling blood glucose measurement as is customary in other smart and non-smart mobile device-based blood glucose meter products on the market.

The Dario BGMS comprises the following components:

- Blood Glucose Meter (BGM) (attaches to a smart mobile)
- Smart Mobile Device Application Software (available on iTunes (Apple)/Google Play (Android))
- Disposable Glucose Test Strips (25 per cartridge)
- Disposable mobile device cover

- Control Solutions (Level 1 and Level 2)
- Lancing Device and Lancets. The Lancing Device provides storage enclosures for the Dario™ Blood Glucose Meter and for the Test Strip cartridge.

Figure 1: Dario Device

[figure not shown]

Figure 2: Dario Device Components

#### 2.4 Device as Provided for Study

The below list of device and components will be provided by LSI for usage in the study.

- Dario BGMS Welcome Kits which include:
  - Dario Blood Glucose Meter (BGM) that attaches to a smart mobile device
  - Dario Lancing Device
  - Dario Lancets
  - Disposable mobile device cover
- Dario Blood Glucose Test Strip Cartridge packs
- Dario lancets
- Dario Control Solution

The subject will be handed with the following equipment and supplies:

- One Dario BGMS Welcome Kit
- Blood Glucose Test Strip Cartridge packs – total of 300 test strips
- 100 Lancets
- Control solutions

Subject will use their own smartphone. Only subjects with supported smartphones will participate in the study.

## 2.5 Device Labeling

The following labeling items are provided when the user receives the Dario:

- Dario™ Blood Glucose Monitoring System User Guide
- Dario™ Blood Glucose Monitoring System Quick Guide with Instructions for Use

All pieces of device labeling will be provided in English.

## 2.6 Dario Digital Platform

Dario digital platform (Dario Engage) provides visibility and reports on patient blood measurement and in the context of the measurement additional user inserted data, such as physical activity, mood, carbs counting, diabetes type, Insulin type etc. The system facilitates 100% data capture with near real-time data synchronization. All cloud stored information enables ubiquitous access of the coach to the system. The coach or any other healthcare provider can then intervene and follow-up the patient's diabetes monitoring to enhance patient motivation and compliance.

# 3.0 Study Objectives

To evaluate the impact of the digital self-monitoring platform provided with diabetes management coaching on:

1. Individual's Quality of life
2. Clinical parameters (HbA1C, weight, lipids profile, etc.)

For adults with Type 2 Diabetes at end of study vs. baseline

## **4.0 Study Design and Procedure**

### **4.1 Study Description**

This study is designed to assess the effect of digital self-monitoring platform used with the remote support of a Health coach on clinical outcomes and Diabetes quality of life. Study design will be an open-label randomized trial of adults with Type 2. Patients are recruited through the Diabetes and Endocrinology Consultants center setting. Upon randomization to the intervention group, study participants will receive three months diabetes health coaching comprising of:

1. Two scheduled phone sessions with a Diabetes health coach a month;
2. Ongoing dual communication with the coach using digital communication channels such as chat, SMS and emails
3. Diabetes education, behavior modification, goal setting and reinforcement.

The Dario App will record participant's glucose measurements and additional information captured by the patient such as medication intake, food and physical activity results. The coach will get access to the patients' App captured information and will intervene ad necessary in the context of the clinical information.

### **4.2 Study Outcome measures**

The following outcomes will be evaluated on subjects that completed the three month coaching program at the end of study vs. baseline.

1. Wellness
  - a. Quality of Life evaluation by questionnaires
2. Clinical outcome
  - a. HbA1C taken in blood test
  - b. Capillary Blood Glucose
  - c. Weight and BMI
  - d. Cardiovascular risk parameters, Lipid panel: Total Cholesterol, Triglyceride, LDL and HDL levels – Blood test
  - e. Blood Pressure

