### **4.3 Study Flow**

- Upon arrival at the study site, potential candidate will be required to complete a CRF (Case Report Form) to verify subject eligibility. If found eligible, the subject

[figure not shown]
will be provided information about the study and consented to participate in the study.

- Subject will be provided with Dario BGMS Welcome Kit, Dario Test Strip Cartridges, lancets and Control Solutions.
- Subject will download the App and register and will conduct the first Dario measurement in the clinic
- Subject will be handed with Coach communication channels page (including coach name, phone number and email address\_
- At this stage the subject has completed the first clinic visit of the study and can start the coaching program.
- The Diabetes health coach will be provided subject's information and will set up the first phone call coaching session with the subject.
- Before the first session the coach will receive a subset of the CRF with the subjects relevant information.
- During the first session, the Diabetes health coach will complete an intake session which includes aspects in Diabetes quality of. The questions express the satisfaction of the patient with managing and controlling diabetes. The items were added according to specific quality of life module ("Development of diabetes-specific quality of life module to be in conjunction with the World Health Organization quality of life scale brief version (WHOQOL-BREF)" Lin et al. *Health and Quality of Life Outcomes* (2017) 15:167). The Diabetes health coach will set up phone calls with the subject on a basis of two times per month for a period of three months.
- During the entire coaching period of three months the Diabetes health coach will have two coaching sessions a months (a total of six session throughout the program) and also will communicate via various communication channels: chat, SMS, email and phone and will drive the coaching based on the data captured by Dario Application including: blood glucose measurements, physical activity, carbs etc. Each coaching session will be recorded in a dedicated coaching summary form as provided in appendix B.
- Following the three months coaching the coach will have a closing session with the subject which will include progress, satisfaction and quality of life questions.
- On day 91 to day 100 the subject will be required to arrive at the Name of Clinic for a venous blood sample administered by a nurse/technician for testing:
  - HbA1C

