### 6.2 Informed Consent

Candidates found eligible for the study will receive an explanation by the investigator or delegate regarding the research nature of the study, the scope and aims of the study, the procedures to be followed and any discomfort that he/she may experience. The candidate will then be asked to read the informed consent form, ask any questions he/she may have and sign the form to indicate consent to participate in the study.

Written informed consent must be obtained from each study candidate. The form should be signed and dated by both the subject and the investigator or delegate. One copy of the signed consent will be given to the subject and the original will be retained by the site.

Subjects may withdraw their consent to participate in the study at any time without prejudice. The investigator may withdraw a subject if, in his clinical judgment, it is in the best interest of the subject or if the subject cannot comply with the protocol. Any withdrawal case should be fully documented in the CRF.

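### Section 4.2 evaluates every outcome only in subjects who completed coaching, and no other analysis set is named, so the before/after change may be biased for the stated objective

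*Combined protocol and SAP*

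**What the plan says.** Section 4.2 sets the population for every listed outcome (quality of life, HbA1c, capillary glucose, weight and BMI, lipids, blood pressure): "The following outcomes will be evaluated on subjects that completed the three month coaching program at the end of study vs. baseline". Section 9.2 adds only that paired tests will compare three-month results with baseline in the same subjects. It gives no analysis set, missing-data rule or sensitivity analysis.

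The objective in section 3.0 is wider: "For adults with Type 2 Diabetes at end of study vs. baseline".

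Losses are expected. Section 9.1 caps enrolment at 25, and the synopsis describes "aiming to have 20 people running the full three months program (after withdrawal"). Under section 6.2 subjects may withdraw consent at any time. The investigator may also withdraw a subject in the subject's best interest or "if the subject cannot comply with the protocol". The same section adds: "Any withdrawal case should be fully documented in the CRF".

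Section 4.3 describes six coaching sessions, after which "the coach will have a closing session with the subject which will include progress, satisfaction and quality of life questions". It puts the first quality-of-life questions in the coach's first session. The end visit is not made conditional on finishing coaching: "On day 91 to day 100 the subject will be required to arrive at the Name of Clinic for a venous blood sample". The synopsis says that at the end of the study "the subject will complete a diabetes quality of life questionnaire and have a blood test".

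**The concern.** The intervention is behavioural, so selecting subjects who finished it selects on engagement with the thing being tested. Selection takes place after baseline, and one of the three withdrawal routes in section 6.2 is inability to comply. If those who stop improve less than those who finish, or worsen, the reported change is too favourable as an answer to the section 3.0 objective. Section 9.2 plans only before/after comparisons, so no between-group contrast would reveal or offset this.

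Three details add to the problem:

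- **'Completed' is undefined.** A subject who attends four of the six sessions could be counted either way, and the choice could be made after the data are seen.
- **Observed values can be excluded.** As worded, section 4.2 leaves out the end values of any subject who stopped coaching but still attended on day 91 to 100.
- **Quality of life depends on coaching attendance.** Section 4.3 places both the first and the closing questions in coaching sessions. A subject who never starts coaching may lack a baseline value, and one who stops may lack an end value.

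**Working it through.** **The plan's own figures.** The ceiling is 25 enrolled and the aim is 20 completing, so the implied loss is L = 1 − 20/25 = 0.20. The reverse step, 20/(1 − 0.20) = 25, agrees but is circular because both use the same two numbers. Section 9.1 states no significance level, power, effect size or standard deviation, so 25 cannot be derived independently.

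**Completer mean against all-enrolled mean.** Let f be the mean change in non-completers as a multiple of the mean change in completers (negative means worsening). Then

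completer mean / all-enrolled mean = 1 / ((1 − L) + L·f).

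The documents give no value for f, so a range is assumed. The losses of 10% and 30% are also assumptions.

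| f | L = 0.10 | L = 0.20 | L = 0.30 |
|---|---|---|---|
| −0.5 | 1.18 | 1/0.70 = 1.43 | 1.82 |
| 0 | 1.11 | 1/0.80 = 1.25 | 1.43 |
| 0.5 | 1.05 | 1/0.90 = 1.11 | 1.18 |
| 1 | 1.00 | 1.00 | 1.00 |
| 1.5 | 0.95 | 1/1.10 = 0.91 | 0.87 |

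For an assumed completer HbA1c change of −1.0 point and L = 0.20, the all-enrolled mean is −0.70, −0.80, −0.90, −1.00 or −1.10, from the top row down.

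**Effect on the test.** An illustrative simulation used 25 subjects with no true change. The five with the lowest latent adherence were dropped and a two-sided paired t-test at 0.05 was run on the other 20. With an assumed correlation between adherence and change of 0, 0.2, 0.3 or 0.5, the completer mean was about 0.00, 0.07, 0.10 or 0.17 SD towards improvement. The test rejected in 5.0%, 6.1%, 7.5% or 12.7% of runs. With all 25 analysed, it rejected in about 5%.

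**How far an available-case analysis helps.** Suppose k of the five non-completers provide an end value and the completer change is −1.0. The estimate is −(20 + k·f)/(20 + k). At f = 0:

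- k = 0: −1.00, the same as the completer analysis
- k = 3: −20/23 = −0.87, which is 0.87/0.80 = 1.09 times the all-enrolled value
- k = 5: −20/25 = −0.80, the all-enrolled value

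**Why a no-change analysis is not a bound.** With k = 0 it gives −20/25 = −0.80 whatever f is. The all-enrolled value would be −0.70 at f = −0.5 and −1.00 at f = 1, so the scenario can be too favourable or too unfavourable.

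**The case against.** The strongest case on the other side has five parts.

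- **Direction is not shown.** A reader might infer that the plan will overstate improvement. The documents do not support that. They contain no data on non-completers, the bias is zero at f = 1, and it reverses above 1. Section 6.2 has two withdrawal routes besides non-compliance, and nothing says how many losses each would produce. This stands: overstatement is plausible, no more.
- **'Completed' may mean reaching three months.** On that reading, the section 4.2 set could largely coincide with the available pairs in section 9.2. The synopsis also attributes the expected losses to withdrawal, and the protocol never describes subjects who stop coaching but stay in the study. This is a fair reading, but the text does not settle it, which is itself a reason to define the term.
- **The quality-of-life passages need not conflict.** A reader might infer that the synopsis, section 4.3 and section 10.3 contradict each other on where the end value is obtained. They do not. The synopsis names no place, and section 10.3 concerns data entry. All three can hold together, and the flowchart and CRF, which cannot be seen here, may add detail. What remains is that section 4.3 ties both sets of questions to coaching sessions.
- **An available-case analysis does not cover everyone enrolled.** If all five lost subjects have no end value, it equals the completer analysis. This stands, and it is why a sensitivity scenario is needed as well.
- **The study is small and open about its rule.** Appendix A calls it a pilot, no hypothesis or power is stated, and the restriction is disclosed. This limits the weight of the point, but the objective is still worded for adults with type 2 diabetes, not for finishers.

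**Conclusion.** The point holds in this form. Section 4.2 restricts every outcome to coaching completers, section 9.2 offers no alternative, and no analysis including non-completers is planned. The paired change may therefore be biased for the section 3.0 objective, plausibly towards overstating improvement.

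The size is unknown. At the implied 20% loss, the completer mean runs from 43% larger to 9% smaller than the all-enrolled mean over f = −0.5 to 1.5. It is 25% larger if non-completers do not change and equal if they change as completers do. Only the 20% comes from the documents, back-calculated from a ceiling and an aim. The values of f, the other loss rates, the −1.0 point, k and the simulated correlations are assumptions. The figures show what could happen, not that bias is present.

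Confidence is high that no other analysis set is planned, but this does not extend to the direction of bias. The plan should be changed, although the study can run as written.

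**What to change.** **Sections 4.2 and 9.2.** Make the main analysis all enrolled subjects with a baseline and an end value, whether or not coaching was completed, and call it an available-case analysis.

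**Section 4.3.** State that subjects who stop coaching without withdrawing consent are still invited to the day 91 to 100 visit. State that quality-of-life questions are obtained at baseline (before or at the start of coaching) and at or by the end visit, regardless of coaching attendance.

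**Sensitivity analysis.** For missing end values, add a no-change analysis that carries the baseline value forward in all enrolled subjects with a baseline. Describe it as one scenario, not a bound.

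**Completer analysis.** Keep it as supportive, with a stated definition of 'completed' and the number of and reasons for non-completion. Section 6.2 already requires withdrawals to be documented.

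**Cost.** The change needs protocol wording, about five extra end assessments at most if 25 enrol and 20 complete (25 − 20 = 5), and one added analysis. The estimate may be less favourable. End values of subjects who withdraw consent are not recovered.

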### **5.3 Recruitment**

The study is aimed to recruit a total of 25 male and female subjects having Type 2 Diabetes between ages 35 years or older. The recruitment will be performed through the Diabetes and Endocrinology Consultants of Pennsylvania, LLC (Decpa LLC) center. The clinic will identify patients that have done HbA1C test during the last 60 days and has HbA1C level as indicated in the inclusion criteria. These subjects will be approached by the clinic to participate in the study.

Each subject completes the study in 2 visits to the diabetes and endocrinology consultants center. The subject will receive a Diabetes health coaching which will include 2 monthly coaching sessions for a period of three months. The total study duration depends on the ability to enroll 25 subjects and is planned for three to four months.

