## **9.2 Data Analyses**

Data will be analyzed comparing the quality of life and clinical outcome before and after the program.

To assess the outcome of the study, the effect of intervention along with digital self-monitoring will be evaluated. Paired group tests will be applied for comparing the results gathered on the same subjects after three months to the baseline values.

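### Section 4.2 evaluates every outcome only in subjects who completed the coaching program, an undefined group; the main analysis should take all enrolled subjects with a baseline and an end value.

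*Combined protocol and SAP*

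**What the plan says.** Section 4.2 fixes the analysis population for every listed outcome (quality of life, HbA1c, capillary glucose, weight and BMI, lipids, blood pressure): "The following outcomes will be evaluated on subjects that completed the three month coaching program". Section 3.0 words the target without that limit: "For adults with Type 2 Diabetes at end of study vs. baseline".

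Enrolment is up to 25, and the synopsis foresees losses, "aiming to have 20 people running the full three months program (after withdrawal". Section 4.3 plans "a total of six session throughout the program" and adds that "Each coaching session will be recorded in a dedicated coaching summary form" (Appendix B), but sets no minimum attendance. It schedules the end-of-study clinic visit for days 91 to 100 without tying it to sessions attended.

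Section 9.2 gives the method: "Paired group tests will be applied for comparing the results gathered on the same subjects after three months to the baseline values". It names no analysis set, missing-data rule or sensitivity analysis. Section 6.2 lets the investigator withdraw a subject in the subject's best interest or "if the subject cannot comply with the protocol". Withdrawals are documented in the CRF, and no end assessment is described for them.

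The CRF and the flowchart are not visible, so all of this concerns the visible text.

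**The concern.** The intervention is engagement with a coach and with self-testing. Selecting those who completed the coaching can mean selecting those in whom the intervention took hold. The synopsis gives a single-arm design and section 9.2 compares only before with after. (Section 4.1 mentions randomization, but no comparison group is described.) So no control group would show the effect of the selection.

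The subjects at issue stop coaching, do not withdraw, and attend the end visit. They have the paired values that section 9.2 needs, yet section 4.2 can leave them out. Because completed has no rule, the decision on a subject with, say, two or four of the six sessions could be made after results are known. The study is open-label, and the sponsor handles data management and statistics.

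**Working it through.** **The plan's own figures.** Section 9.1 states up to 25 subjects with no derivation. The only possible check is consistency: 20/(1 − 0.20) = 25. The 20% is itself read off 25 and 20, (25 − 20)/25, and is not a stated dropout rate.

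**Bias formula.** Inputs: 25 enrolled (documents); k left out and d HbA1c points worse (both assumptions, since the documents give neither). Completers change by c, the others by c + d.

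- Completer mean = c
- All-enrolled mean = [(25 − k)c + k(c + d)]/25 = c + (k/25)d
- Excess improvement reported = (k/25)d

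| k | d = 0.5 | d = 1.0 |
|---|---|---|
| 1 | 0.02 | 0.04 |
| 3 | 0.06 | 0.12 |
| 5 | 0.10 | 0.20 |
| 10 | 0.20 | 0.40 |

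**Scale.** For an assumed SD of change of 1.0 to 2.0, the standard error of the completer mean is:

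- 20 completers (k = 5): 1.0/√20 = 0.22 to 2.0/√20 = 0.45
- 15 completers (k = 10): 1.0/√15 = 0.26 to 2.0/√15 = 0.52

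The excess is below one standard error at k = 5. At k = 10, d = 1.0 and SD 1.0 it is not (0.40 against 0.26).

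**What the remedy recovers.** If r of the k return for the end visit and are typical of the k, the analysed mean is c + rd/(25 − k + r). The excess left is d[k/25 − r/(25 − k + r)]. For k = 5:

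| r | calculation | d = 0.5 | d = 1.0 |
|---|---|---|---|
| 1 | 0.200 − 1/21 | 0.076 | 0.152 |
| 3 | 0.200 − 3/23 | 0.035 | 0.070 |
| 5 | 0.200 − 5/25 | 0 | 0 |

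If those who return do better than those who do not, less bias is removed than shown.

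**Precision.** The analysed number cannot fall, because every completer with paired values stays in. The 95% confidence half-width is 0.47 SD at n = 20, 0.44 SD at n = 22 and 0.41 SD at n = 25.

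**The case against.** The strongest reply is that the restriction may remove almost nobody. The synopsis wording links the 20 to those remaining after withdrawal. On that reading non-completers are mainly people who left, paired tests could not use them anyway, and the proposed set nearly equals the one in section 4.2. The end visit is already unconditional, section 6.2 does not say that stopping coaching is withdrawal, and the completer population is openly stated in a small single-site study. All of this stands. It limits the likely size, but it does not supply the missing definition or an all-enrolled analysis.

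A reader might infer several stronger points that the documents do not support:

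- **That at most five subjects can be lost, so the bias must be below random error.** The 20 is an aim, not a bound, and the table above gives a counterexample. Nor does a confidence interval account for selection.
- **That section 5.3 contradicts section 4.2.** "Each subject completes the study in 2 visits" concerns completing the study; section 4.2 concerns completing the coaching program.
- **That section 3.0 conflicts with section 4.2.** An objective names a target population and need not fix an analysis set. The gap is that the analysed group is narrower, with nothing alongside it.
- **That quality of life can be rescued by asking at the clinic visit.** Section 4.3 places the intake questions in the first coaching session, so a subject who never starts may have no baseline. Asking only non-completers at the clinic would confound mode with completion.

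**Conclusion.** The point holds as a modest one. Section 4.2 states a restricted analysis population without a rule for membership, and a less selective alternative is available from a visit already planned. The direction of bias rests on the assumption that those who stop coaching do worse. Its size rests on assumed k and d: 0.02 to 0.20 HbA1c points for k = 1 to 5, and 0.40 for k = 10 with d = 1.0. The number who stop coaching yet have end values is unknown and may be small.

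A reader might conclude that the study's result is overstated. Nothing in the documents shows that, or that any conclusion would change. A completer estimate is legitimate as a secondary result. The importance is minor to moderate.

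**What to change.** - **Section 4.2:** make the main analysis all enrolled subjects with a baseline and an end value, whatever their coaching attendance. Keep completers as a secondary analysis, defined in advance by a minimum number of the six sessions as counted on the Appendix B forms.
- **Sections 6.2 and 4.3:** state that stopping coaching is not study withdrawal, and that the existing day 91 to 100 visit applies to every subject who has not withdrawn. Leave consent and best-interest withdrawal unchanged.
- **Section 9.2:** report the number and baseline values of enrolled subjects without end values, and add a simple sensitivity analysis that assigns them no change. For illustration, if 20 subjects average −1.0 and 5 are missing, the mean becomes (20 × −1.0 + 5 × 0)/25 = −0.80.
- **Scope:** apply this mainly to HbA1c, lipids, weight/BMI and blood pressure. For quality of life, analyse subjects with both coach-administered values and report how many lack them.

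The session forms and the visit already exist. The costs are a protocol amendment submitted to the IRB (section 7.5), recalling a few subjects, and possibly a smaller mean change. Subjects who do not return stay missing, so the bias is reduced but not removed.
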